## 11.2 Serious Adverse Reactions and Unexpected Adverse Reactions

### 11.2.1 Definitions

#### ***Adverse Reaction:***

All noxious and unintended responses to a medicinal product related to any dose should be considered adverse drug reactions.

The phrase “responses to a medicinal product” means that a causal relationship between a medicinal product and an AE is at least a reasonable possibility, i.e. the relationship cannot be ruled out.

For marketed medicinal products, an adverse reaction is a response to a drug which is noxious and unintended and which occurs at doses normally used in man for prophylaxis, diagnosis, or therapy of disease or for modification of physiological function.

#### ***Unexpected Adverse Reaction:***

An unexpected adverse reaction is defined as an adverse reaction, the nature or severity of which is not consistent with the applicable product information (e.g. IB for an unauthorised IMP or similar product information sheet such as the SPC).

#### ***Suspected Unexpected Serious Adverse Reaction (SUSAR):***

A SUSAR is defined as any serious adverse reaction that might be related to the IMP and is unexpected according to the definition above.

### 11.2.2 Reporting of suspected unexpected serious adverse reactions

SUSARs will be reported by the PV CRO according to appropriate competent authority and EC requirements. SUSARs will be reported to Investigators according to ICH GCP and to local regulations. SUSAR reporting to competent authorities and ECs will be performed according to local regulations in an unblinded manner. The competent authorities will be notified of all SUSARs through the EudraVigilance database.

Fatal and life-threatening SUSARs should be reported by the PV CRO as soon as possible to the competent authorities and ECs according to local regulations, and, in any case, no later than seven calendar days after knowledge by the PV CRO of such a case. Relevant follow-up information on the case will be subsequently communicated within an additional eight days. All other SUSARs shall be reported to the competent authorities and ECs according to local regulations as soon as possible but within a maximum of fifteen days of first knowledge by the PV CRO.

## 11.3 Drug Induced Liver Injury (DILI)

### 11.3.1 Severe drug-induced liver injury

Irrespective of perceived causation, in the event of severe drug-induced liver injury (DILI) then the investigational drug should be discontinued until the episode is deemed to have resolved. In the event the investigational drug is deemed to be the cause of the liver injury then the patient should not be re-challenged with the drug.

Potential severe DILI in the study population (severe acute decompensated AH patients with impaired baseline liver biochemistry) stipulates evidence of hepatic impairment as demonstrated by:

- Total bilirubin >2x baseline and ALT and/or AST >3x baseline (confirmed by immediate repeat testing)
- Total bilirubin >3x baseline (confirmed by immediate repeat testing)
- ALT and/or AST >5x baseline (confirmed by immediate repeat testing)
- ALT and/or AST >500 U/L (confirmed by immediate repeat testing)
- Alkaline Phosphatase  $\geq$ 5x baseline
- An increase in MELD score > 10
- Lille score > 0.85

Prompt (within 24 hours) adjudication of events of possible DILI or treatment failure, as listed above, will be performed by an independent expert in AH and DILI with recommendations for or against drug discontinuation.

Other causal factors should be considered and if found they must be discussed with the sponsor before investigational product is restarted.

Even if patients discontinue the investigational drug they should still be encouraged to attend study visits for continued study data collection.

### 11.3.2 Monitoring of patients with impaired liver biochemistry

Abnormalities of liver biochemistry indicating evidence of hepatic impairment as listed above should be followed by repeat testing within 48-72 hours to confirm/determine if the biochemical changes are improving or worsening. AE information should be collected alongside a thorough physical examination. A liver aetiology screen and/or other appropriate testing should be undertaken. In the event of liver dysfunction then the patient should be managed as a severe drug-induced liver injury (see above). Pausing of drug treatment should be considered if any of the criteria in the previous section occur.

## 11.4 Pregnancy Reporting

If a patient or a patient's partner becomes pregnant during the study, study staff must be

---

informed as soon as possible. Upon confirmation of the pregnancy, the patient must be withdrawn from the study drug but may continue study participation. The Investigator must complete a study-specific pregnancy form upon confirmation of a pregnancy and send it to the Sponsor within 24 hours of confirmation of the pregnancy.

Post-treatment follow-up should be done to ensure patient safety. Pregnancy itself is not an AE or SAE, however maternal/foetal complications or abnormalities will be recorded as AEs or SAEs, as appropriate. The Investigator will follow the pregnancy until completion (or until pregnancy termination) and notify the Sponsor of the outcome as a follow up to the initial pregnancy form.

## 12 STATISTICAL METHODOLOGY AND DATA MANAGEMENT

### 12.1 Study Design

This clinical trial employs a randomised, double-blind, placebo-controlled 2-arm parallel group design preceded by an open-label pilot phase. Randomisation is used to minimise assignment bias and to increase the likelihood that known and unknown patient attributes (e.g. demographic characteristics) are evenly balanced across the treatment groups. Blinding is used to reduce potential bias during data collection and the evaluation of safety and efficacy. The use of placebo as a comparator is justified as a reasonable design to assess safety and efficacy in patients based on the brevity of the study duration and the absence of any real established standard of care for alcoholic hepatitis. A full description of the study design is presented in Section 6 above.

### 12.2 Randomisation

For the open label pharmacokinetic pilot phase, six patients will be enrolled and treated with study drug (2 x DS102 500mg capsules orally administered BD (four capsules daily)), for 28 days. Results of this pilot phase will be assessed by a DSMB for safety and if dose adjustments for the main study are needed.

For the main, double-blind phase, approximately 120 patients will be randomised into double-blind treatment groups in a 1:1 ratio as follows:

- Treatment group A: 2 x placebo 500mg capsules orally administered BD (four capsules daily) for 28 days
- Treatment group B: 2 x DS102 500mg capsules orally administered BD (four capsules daily) for 28 days

At the investigational site, each patient will be assigned a patient screening number during screening that will be used on all patient documentation. The patient screening number will contain the site number and the patient number assigned in numerical order at the screening visit (e.g.: 02-010 for the tenth patient screened at the site #02). Numbers will be assigned in ascending order starting with 001.

A randomisation list, permuted blocks and stratified by site, will be generated by Afimmune or its designee. The randomisation schedule with study drug assignments will be generated prior to the start of the study and will be known only to the individuals responsible for labelling the study drug, the statisticians generating the schedule and the interactive web response system (IWRS) team responsible for implementing the schedule. The IWRS will assign medication kit numbers to each patient, as required, at visits and the contents will be based on the randomisation code.

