## 12.3 Estimation of Sample Size

### Two-Sample T-Tests using Effect Size

#### Numeric Results for Two-Sample T-Test

Alternative Hypothesis: H1:  $d \neq 0$

Target Power	Actual Power	Effect Size				Alpha
		N1	N2	N	d	
0.80	0.8036	100	100	200	0.40	0.050
0.80	0.8002	90	90	180	0.42	0.050
0.80	0.8045	83	83	166	0.44	0.050
0.80	0.8044	76	76	152	0.46	0.050
0.80	0.8051	70	70	140	0.48	0.050
0.80	0.8015	64	64	128	0.50	0.050
0.80	0.8065	60	60	120	0.52	0.050
0.80	0.8014	55	55	110	0.54	0.050
0.80	0.8074	52	52	104	0.56	0.050
0.80	0.8030	48	48	96	0.58	0.050
0.80	0.8037	45	45	90	0.60	0.050

To discover an effect size of 0.54 (=Difference in means/standard deviation) in MELD change from baseline with 80% power, 55 patients per group are necessary under ideal assumptions using the t-test for independent samples (alpha=0.05, two-sided).

To take deviations from ideal parametric conditions and drop-outs into account randomisation of 60 patients per group is recommended.

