### **12.8.2 Primary Variables**

The primary efficacy variable will be change in MELD score from baseline to Day 28. This change in MELD score and its difference between treatment groups will be estimated using a General Linear Repeated Measures Model with treatment arm, baseline MELD value, visit and treatment arm by visit interaction as factors. The primary analysis will be based on the FAS and repeated for the PPS as a supportive analysis.

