2.3 Study Design

This is a randomised, placebo-controlled, double-blind, parallel group, multicentre, exploratory phase II study preceded by an open label pilot phase to investigate the efficacy and safety of orally administered DS102 capsules in patients with acute decompensated AH aged over 18 years. Patients will be recruited from 50 sites across 9 countries.

The open label pilot phase is a single arm study, all 6 patients will receive study drug (2 x DS102 500mg capsules orally administered twice a day (BD) (four capsules daily)), for 28 days. Results of the pilot phase will be assessed by a data and safety monitoring board (DSMB) for safety and if dose adjustments for the main study are needed.

After the open-label pilot phase of the study, two parallel groups of patients will be enrolled into the randomised double-blind phase of the study to compare one dose of DS102 with placebo over a 28-day treatment period. Patients will receive standard of care therapy in addition to their assigned investigational medicinal product (IMP)

throughout the treatment period of the study. It is planned that 120 evaluable patients, 60 per treatment group, will be randomised.

The study population will consist of male and female patients diagnosed with severe acute decompensated AH aged 18 years and over.

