6.11.1 Primary Analysis

Percentage change in MELD score from baseline up to and including day 28 will be assessed by modelling change from baseline with a mixed-model repeated measures (MMRM) analysis, using the FAS, including terms for treatment group, visit, treatment-by-visit interaction as fixed effects and the baseline MELD value as a covariate. The adjusted treatment least squares (LS) means and adjusted mean LS difference between the active dose and placebo will be presented along with 95% confidence intervals (CI) and p-value for the day 28 timepoint. Early termination data will be entered into the model at the next scheduled visit following the date of termination, not at day 28.

F-tests from PROC MIXED will be based on Kenward-Roger's adjusted degrees of freedom. The following variance/covariance matrix structures for the repeated visits within a patient will be assessed: Compound symmetry, 1st order autoregressive, Toeplitz and unstructured. The variance/covariance matrix structure that results in the smallest Akaike's information criterion (AIC), indicating the best model fit will be selected.

Assumptions of normality will be assessed visually using diagnostic plots. Should assumptions of normality not hold the model will be fitted to the change from baseline of log-transformed data. Should the assumptions behind the model still not hold an alternative approach to the analysis will be decided following the BDRM and will be detailed in a SAP amendment.

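### Randomisation is stratified by site but the primary MMRM has no site term, so the test is mildly conservative if sites differ; a random site intercept would correct this

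*Protocol*

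**What the plan says.** Protocol 12.2 describes the list: "A randomisation list, permuted blocks and stratified by site, will be generated by Afimmune or its designee". No other stratification factor is named and no block size is given. The same section says that "approximately 120 patients will be randomised into double-blind treatment groups in a 1:1 ratio as follows". SAP 2.3 adds: "Patients will be recruited from 50 sites across 9 countries".

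Protocol 12.8.2 specifies a "General Linear Repeated Measures Model with treatment arm, baseline MELD value, visit and treatment arm by visit interaction as factors". SAP 6.11.1 specifies an MMRM on the FAS, "including terms for treatment group, visit, treatment-by-visit interaction as fixed effects and the baseline MELD value as a covariate". It uses Kenward-Roger degrees of freedom and chooses among four within-patient covariance structures by AIC. Neither model has a site or country term.

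The sensitivity analyses in SAP 6.11.2 are the per-protocol set and last observation carried forward; neither adds site. SAP section 4 does not repeat the stratification, and the list of departures from the protocol in SAP 6.25 does not mention centre. No reason for leaving site out and no rule for small sites appear in either document.

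**The concern.** An analysis should normally reflect the factor by which the trial randomises. Permuted blocks within site push the arms towards balance at each site, which takes part of the between-site variation out of the treatment comparison. A model without site still counts that variation as residual noise. Its standard error then describes a less precise trial than the one run: intervals are too wide and the test rejects too seldom under the null.

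Site differences are plausible. Background care is left largely to the investigator, and Protocol 12.1 justifies placebo partly by the lack of an established standard of care. The central laboratory limits assay differences but not differences in care or case mix. At stake is some efficiency and calibration in a trial sized with little margin.

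**Working it through.** **1. Inputs from the documents.** About 120 patients randomised 1:1; 50 sites, so 120/50 = 2.4 patients per site; 9 countries, so 120/9 = 13.3 per country. Effect size d = 0.54 with 55 per group, raised to 60 per group for non-ideal conditions and drop-outs (Protocol 12.3), an allowance of 5/60 = 8.3%.

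**2. Assumptions, because the documents give no figure.** Share of outcome variance lying between sites (ICC, ρ) from 0 to 0.20; block size 2 or 4; unequal site sizes.

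**3. The plan's own figure.** The two-sample t-test has noncentrality d × √(n/2) = 0.54 × √27.5 = 2.832, with 108 degrees of freedom and critical value 1.982. Power is 0.8014, exactly as in Protocol 12.3; all 11 rows of that table reproduce to four decimals. With 60 per group and no losses, power is 0.835. The calculation claims no benefit from stratification.

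**4. Direction and upper limit of the effect.** Take unit outcome variance and N = 120.
- SE reported by a model without site: about √(4/N) = √(4/120) = 0.183.
- True SE if the arms were perfectly balanced within every site: √(4(1−ρ)/N).
- Overstatement of the SE: 1/√(1−ρ).
- Resulting type I error: about 2Φ(−1.96/√(1−ρ)).

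| ρ | True SE, perfect balance | SE overstated by | Type I error |
|---|---|---|---|
| 0.05 | 0.178 | 2.6% | 4.4% |
| 0.10 | 0.173 | 5.4% | 3.9% |
| 0.20 | 0.163 | 11.8% | 2.8% |

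With 2.4 patients per site many blocks stay incomplete and balance is only partial, so the real effect should generally be smaller.

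**5. Simulation.** 120 patients, 50 unequal sites, site-stratified blocks, one Day 28 outcome, random site intercept fitted by REML. Set A has 2000 trials per setting, set B 3000 (blocks of 4) and set C 1000 (blocks of 4). In set A with blocks of 4, model SE against true SE was 0.183 vs 0.183 at ρ = 0, 0.182 vs 0.176 at 0.05, 0.183 vs 0.177 at 0.10 and 0.182 vs 0.169 at 0.20.

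Type I error (%), without → with the random site term:

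| ρ | A, blocks of 2 | A, blocks of 4 | B |
|---|---|---|---|
| 0 | 5.5 → 5.9 | 6.2 → 6.5 | 5.1 → 5.3 |
| 0.05 | 4.6 → 5.1 | 4.8 → 5.4 | not run |
| 0.10 | 3.5 → 4.8 | 4.3 → 4.8 | 4.1 → 5.0 |
| 0.20 | 3.0 → 5.0 | 3.3 → 4.8 | 3.8 → 5.3 |

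Simulation error in set A is about 0.5 points. The set A values at ρ = 0 are therefore somewhat high by chance: the unadjusted test is correct there.

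Power (%) at d = 0.54, without → with:

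| ρ | A, blocks of 2 | A, blocks of 4 | B | C |
|---|---|---|---|---|
| 0 | 83.8 → 84.2 | 83 → 83 | 85 → 86 | – |
| 0.05 | 84.5 → 85.4 | 85 → 86 | – | 82.2 → 83.9 |
| 0.10 | 83.6 → 85.5 | 83 → 86 | 84 → 86 | 85.2 → 86.1 |
| 0.20 | 85.5 → 89.4 | 84 → 88 | 85 → 89 | 84.5 → 88.3 |

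Simulation error is about 0.8 points per figure in set A and about 1 point in set C. The gain is about 0, 1, 1 to 2.5 and 4 points.

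**6. Alternatives, set A.** Fixed site effects lost about 5 to 6 points of power at ρ = 0 and 3 to 6 at 0.05; with unequal sites they gained at most 1.5 points at 0.20. Fixed country effects moved power by no more than about 2 points either way.

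**The case against.** The strongest case for leaving the plan alone has four parts.

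**Nothing claimed is undermined.** The error is in the safe direction and the stated power comes from an unadjusted test. This stands. A reader might infer that ignoring the stratification invalidates the test or overstates the 80% power. The documents support neither reading.

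**The loss is not shown.** It depends on a between-site variance and a block size that are not stated, and only ρ = 0.20 gives a gain clearly beyond simulation error. The simulations also leave out baseline MELD, repeated visits, deaths and drop-outs, and baseline adjustment may already absorb part of any difference in case mix. This stands too. A reader might infer that the plan certainly gives power away; the documents show only that it may, if sites differ.

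**The site variance will often be estimated as zero.** In set C this happened in about 57% of trials at ρ = 0, 33% at 0.05 and 15% at 0.10, so the data would often choose the model. This carries less weight. With a zero site variance, the treatment estimate and its model-based SE equal those of the model without site, so reporting the simpler model is not a real choice between results.

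**The change is more than one line.** The SAP must say how the site term sits beside the AIC selection. In the logistic models a random intercept would also change the odds ratio being estimated. Both points stand and limit the fix.

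A reader might also infer from the nine countries that a country term is owed. Country is not a stratification factor, so omitting it does not depart from the randomisation.

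**Conclusion.** The mismatch between design and analysis is real and unexplained, but its consequence is modest and conditional. If sites differ, the planned SE is somewhat too large and the test mildly conservative: type I error of about 4% at an ICC of 0.10 and 3 to 4% at 0.20. If sites are alike, nothing is lost. The estimate is not biased, the error rate is not inflated and the stated 80% power holds.

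A random site intercept costs essentially nothing at ICC 0 and brings the test back to about 5% when sites differ. The power figures rest on the assumed ICC, block size and site sizes, and on a single-visit simulation. They are better read as upper expectations for the full MMRM, since baseline MELD may remove part of the site variation. One intercept shared by all visits would also capture less if site differences change over time.

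**What to change.** Amend SAP 6.11.1 before unblinding; the blinded data review in SAP 6.2 provides a route.

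- Add a random intercept for site to the primary MMRM and to the continuous-outcome secondary MMRMs. Keep it alongside the within-patient covariance structure, so that AIC still chooses only among the four structures already listed.
- State the rule in advance: if the site variance is estimated as zero or the model does not converge, the model without site is reported.
- Do not use fixed site effects, and do not present fixed country effects as an equivalent fallback.
- Do not extend the term automatically to the binary and ordinal logistic models. Decide there separately, since the odds ratio would change meaning.
- Repeat the stratification factor in SAP section 4 and record the added term in SAP 6.25.

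The cost is a few sentences of text, slightly more model-fitting work and some risk of non-convergence, which the rule covers. The sample size needs no change.

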## 12.3 Estimation of Sample Size

### Two-Sample T-Tests using Effect Size

#### Numeric Results for Two-Sample T-Test

Alternative Hypothesis: H1:  $d \neq 0$

Target Power	Actual Power	Effect Size				Alpha
		N1	N2	N	d	
0.80	0.8036	100	100	200	0.40	0.050
0.80	0.8002	90	90	180	0.42	0.050
0.80	0.8045	83	83	166	0.44	0.050
0.80	0.8044	76	76	152	0.46	0.050
0.80	0.8051	70	70	140	0.48	0.050
0.80	0.8015	64	64	128	0.50	0.050
0.80	0.8065	60	60	120	0.52	0.050
0.80	0.8014	55	55	110	0.54	0.050
0.80	0.8074	52	52	104	0.56	0.050
0.80	0.8030	48	48	96	0.58	0.050
0.80	0.8037	45	45	90	0.60	0.050

To discover an effect size of 0.54 (=Difference in means/standard deviation) in MELD change from baseline with 80% power, 55 patients per group are necessary under ideal assumptions using the t-test for independent samples (alpha=0.05, two-sided).

To take deviations from ideal parametric conditions and drop-outs into account randomisation of 60 patients per group is recommended.

## 12.4 Blinding and Code Breaking Instructions

All study site personnel, as well as the personnel involved in the monitoring or conduct of the study, will be blinded to the individual patient treatment assignments. Randomisation details will be kept strictly confidential, accessible only in an emergency to authorised persons, until the time of formal unblinding. The blinded code for the trial will be broken only after all patient data has been recorded and verified and the database locked.

Emergency unblinding will be performed via the IWRS, with relevant site personnel and PV monitors provided with the required system access to carry out unblinding.

## 12.5 Data Analysis

Data analysis will be performed at the CRO. All computations will be completed using SAS® version 9.1.3 or later. Graphical summaries will be produced using SAS®. A detailed description of the analyses to be performed will be provided in the Statistical Analysis Plan (SAP).

## 12.6 Analysis Populations

### **Full Analysis Set (FAS):**

Patients will be included in the FAS for analysis of efficacy if they are randomised to the study and received at least one dose of study medication. The specific criteria for the FAS will be detailed in a separate SAP. Analysis will be done according to treatment as randomised.

### **Safety Analysis Set (SAS)**

The SAS consists of all patients who received at least one dose of the medication. SAS is the analysis population for all safety endpoints. Analysis will be done according to the actual treatment patients received.

### **Pharmacokinetic Population**

The PK population consists of all patients who received at least one dose of study medication.

### **Per Protocol Set:**

In order to qualify for the Per Protocol Set (PPS), the patients must have followed the study protocol without any major protocol deviation. Protocol violations will be assessed for each patient in a blinded fashion prior to database lock at a Blind Data Review Meeting (BDRM), and the PPS will also be finalised during this meeting. PPS is a supportive analysis population for the primary efficacy endpoint. Analysis will be done according to the treatment that patients were randomised to.

